Protocol

Objective. The primary objective of the current IRB application is to define the time course of change in pain score after 5 min heating of the skin applied at intervals during and following infusion of intravenous oxytocin in order to create a PK/PD model for oxytocin-induced analgesia. The proposed study design will advance the preliminary data by use of a dosing regimen predicted to produce the maximum achievable effect with oxytocin in a manner that will validate and more precisely describe PK/PD model from preliminary data.

A secondary objective is to test for effects of subject sex or age on oxytocin effect.

Overview. Equal numbers of adult men and women, age 18-75 will be recruited. Subjects will report to the Pain Clinical Research Unit (CRU) or the CTSI CRU for four visits, the first to confirm consent and train the individuals in all heat pain procedures, the second to infuse oxytocin intravenously, record heat pain ratings at 15 min intervals for 2 hr, then once more at 3 hr, and the third and fourth to record heat pain ratings approximately 24 hr and 5-7 days after oxytocin infusion. A PK/PD model will be generated from these PD measures (heat pain ratings). We will not withdraw blood and measure oxytocin for PK in these subjects nor in subsequent studies to be submitted to the IRB. Rather, we will use the population PK model of intravenous oxytocin established from a past study of 11 volunteers and an ongoing study in 24 other volunteers.

[figure not shown]

Figure 1. **A)** plasma oxytocin concentrations with LC/MS (red/black lines) compared to plasma by RIA (blue lines. **B)** modeled plasma oxytocin concentrations (blue line) and observed (circles) and modeled (green dash) pain scores after 10 min infusion of 17 μ g oxytocin. **C)** as in B) but after 30 min infusion of 14 μ g oxytocin

Phase II trials

Setting

The training visit will occur at either the Pain CRU at Piedmont Plaza 2 or the CTSI CRU. Drug study visits will occur on the main campus at CTSI CRU.

Subjects selection criteria

The study will enroll healthy subjects.

Inclusion Criteria

1. Male or female ≥ 18 and < 75 years of age, Body Mass Index (BMI) <40 .
2. Generally in good health as determined by the Principal Investigator based on prior medical history, and as assessed to be American Society of Anesthesiologists physical status 1, 2

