The projected sample size is 24 evaluable subjects with complete data sets. We request to enroll up to 26 subjects. Our current estimates indicate that the confidence interval for studies of 21 individuals with pain intensity ratings in two preliminary studies will determine the pharmacodynamic parameters with a corrected confidence range < 20%. A corrected confidence range < 20% implies that mixed effect analysis will distinguish covariate effects in the range of 40% in a study with 21 or more subjects. This is the range at which the covariate effect may be clinically consequential. In practice, mixed-effects analysis with NONMEM is often sensitive to covariate effects smaller than predicted by preliminary analyses. The sample size is increased to 24 to provide covariate assessment for age, weight, and sex.

Interventions and Interactions

At all study visits participants will be queried regarding recent history of symptoms commonly associated with COVID-19 or recent close contacts with anyone with a positive COVID-19 test.

Study Visit 1:

The participant will report to the Pain CRU or the Wake Forest CTSI CRU. The participant will review and sign the Informed Consent. After informed consent is adequately obtained, a detailed medical history will be obtained from the participant, female participants will have a urine pregnancy test performed to determine pregnancy status. Vital signs to include blood pressure (BP), heart rate (HR), respiratory rate (Resp) and oxyhemoglobin saturation by pulse oximetry (POX) will be measured and recorded along with height and weight.

Once eligibility has been determined the participant will be trained in study procedures. This will include pain ratings to brief (5 sec) heat stimuli on the lateral calf to 39, 41, 43, 45, 47, and 49°C and then a pain intensity rating each minute for 5 mins during heating to 45°C. If the pain report to 45°C is ≤ 2 at the end of the 5 min, a second trial using 46°C will be done. If the 46°C results in pain intensity ≤ 2, a third trial with 47°C will be performed, and if that trial results in pain intensity ≤ 2, a third trial with 48°C will be performed. Subjects who have pain intensity ≤ 2 with the 48°C 5-min stimulus will not be further studied. The duration for visit 2 will be approximately 2 hours.

Study Visit 2

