- c. Pulse oximetry less than 94% that does not correct with several deep breaths.

Treatment of BP elevations > 20% of baseline will be treated with labetalol 5-15 mg IV incrementally until BP elevation <20% elevated. Treatment of symptomatic hypotension or BP reductions >20% will be treated with incremental ephedrine 5-20 mg, IV. Heart rate (HR) reductions or elevations > 20% of baseline will be treated with incremental glycopyrrolate 0.2 mg IV or propranolol 0.2 mg IV, respectively. Peripheral oxyhemoglobin desaturation (< 90) will be treated with supplemental oxygen, nasal cannula, face mask, or non-rebreathing mask depending upon the degree desaturation and the response to therapy.

Regardless of whether any treatment is required, subjects with significant side effects will be monitored more frequently (every 5 min for BP and HR; continuously for POX) until symptoms or signs resolve.

Serious adverse events: In addition to treatment, as described above, and timely reporting as required to the DSMC, IRB, and FDA, emergency treatment will be available within the CRU itself. As such, an ACLS-certified health care professional will be on site or within 5 minutes of the CRU during each treatment session, and a crash cart containing medicine and equipment for emergency resuscitation, and an automated external defibrillator will be located on-site.

Study Stopping Criteria: Should significant cardiorespiratory or other side effects occur during oxytocin administration, the IV infusion will be stopped and the subject treated as indicated in Treatment of Side Effects.

The study will be stopped if more than 2 individuals exhibit significant cardiorespiratory side effects or after any serious adverse event and future conduct of the study will be determined by recommendations from the DSMC, IRB, and FDA.

Outcome Measure(s)

Primary Outcome Measure

Name: Average verbal pain score (0-10) at one min intervals during the 5 min of skin heating

Type: Primary

Time Frame: For 180 minutes after the beginning of oxytocin infusion

Description: Pain scores are measured each minute during 5 min heating of the skin of the calf, with temperature of the probe determined in visit one to obtain a pain score at the end of this period of > 2.

Analytical Plan

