The primary analysis will use NONMEM to create a PK/PD model of oxytocin on average pain ratings each min for 5 min during the noxious heat stimulus. To do so, pain scores over time will first be modeled using NONMEM with derived parameters of maximum effect (Emax), predicted concentrations from the PK/PD model to produce a 50% and 90% maximum drug effect (C50 and C90, respectively), the steepness of the dose response curve (γ), and the time to peak effect. Inter-subject variability (e.g., biological variability) will evaluate additive, proportional, and exponential models. Residual intrasubject variability (e.g., noise) will typically require an additive and multiplicative error model. The influence of covariates (e.g., age, sex, weight) on model parameters will be analyzed by serial inclusion / exclusion, with significance determined by the likelihood ratio test ($p < 0.01$ if the decrease in -2 log likelihood exceeds 6.6 ($\chi^2_{0.99}$, $df = 1$)). Parameters will be estimated using first-order conditional estimate with η - ε interaction.

Covariate effects deemed significant by likelihood ratio test will be validated using jackknife cross-validation [10]. Jackknife cross-validation provides an estimate of the utility of the covariate to inform the pharmacodynamics in a future individual, rather than merely characterize the pharmacodynamics in the individuals from which the model was derived. The jackknife cross-validation divides the data into N subsets. Each subset leaves out a single individual. The parameters of the model are re-estimated for each subset with and without the covariate being validated. The inaccuracy (mean $((|measured - predicted|) / predicted)$), of the model with and without the covariate is measured in the excluded individual. The covariate is only being included in the final model if the improvement in model accuracy in the N iterations is significantly greater than 0. Jackknife cross-validation helps compensate for NONMEM's ability to identify very small covariate effects that do not meaningfully contribute to accuracy in future patients.

Expected outcomes. Based on pain ratings and an estimate of the PK/PD model from preliminary data (Fig 1), we anticipate that the maximum oxytocin effect is a 50-60% reduction in pain rating from the 5 min heat stimulus.

Human Subjects Protection

Subject Recruitment Methods

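### The jackknife gate divides each model's error by that model's own prediction, which tilts it against a covariate that lowers predicted pain; the loss is modest and depends on the gate test

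*Combined protocol and SAP*

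**What the plan says.** The Analytical Plan screens age, sex and weight in two steps. The first is an LRT at p < 0.01. The second is a jackknife: both models are refitted without each subject in turn, and "The inaccuracy (mean $((|measured - predicted|) / predicted)$), of the model with and without the covariate is measured in the excluded individual". The covariate stays only "if the improvement in model accuracy in the N iterations is significantly greater than 0". The stated purpose is to screen out "very small covariate effects that do not meaningfully contribute to accuracy in future patients".

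Three other places bear on this:

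- Objective: "A secondary objective is to test for effects of subject sex or age on oxytocin effect".
- Sample Size: "mixed effect analysis will distinguish covariate effects in the range of 40" per cent with 21 or more subjects, followed by "This is the range at which the covariate effect may be clinically consequential". N was then raised to 24 for the covariate assessment.
- Primary Outcome Measure: the quantity being predicted is "Average verbal pain score (0-10) at one min intervals during the 5 min of skin heating". The Analytical Plan says its residual variability "will typically require an additive and multiplicative error model".

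**The concern.** The two models are compared on different divisors. If a covariate correctly lowers predicted pain in a group, the numerator shrinks because the prediction is closer, but the divisor shrinks too. The ratio can therefore rise although accuracy in pain points has improved. A score of this form is not minimised at the true mean. With true mean 1.70 and SD 1, it is lowest at a prediction of about 2.2.

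A responsive group is one with low pain after oxytocin, and the plan expects a maximum reduction of 50–60%, so predictions will be in the range where this matters. At stake is whether a sex or age effect that has passed the LRT enters the final model. A gate meant to remove effects that do not help prediction can, in part because of its divisor, remove one that does.

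**Working it through.** **1. The plan's own figure.** The 0.99 quantile of chi-square with 1 df is 6.635, which agrees with the stated cut-off of 6.6. The plan gives no power or retention rate for the gate, so there is nothing further to reproduce.

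**2. Inputs from the plan.** There are 24 evaluable subjects in equal numbers of men and women (12 v 12). Ratings are every 15 min to 2 h, then at 3 h. Emax is taken as 0.55, the middle of 50–60%. Sample Size does not say which parameter its 40% concerns. Applied to Emax it gives 0.40 × 0.55 = 0.22, that is 0.44 v 0.66.

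**3. Assumed, because the plan gives no values.** Median baseline 3, 4 or 5; baseline CV 20% or 40%; Emax SD 0.10 or 0.15; residual SD 0.5, or 0.3 plus 20% proportional. This makes 24 scenarios. The time course of effect, population-level predictions for the left-out subject, and the gate test are also assumed.

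**4. Closed form at peak effect.** If a rating is normal with mean m and SD s, and the prediction is p, put d = m − p. Then E|error| = s√(2/π)·exp(−d²/2s²) + d[1 − 2Φ(−d/s)]. Take baseline 5 and s = 1. The prediction without the covariate is 5 × 0.45 = 2.25. With it, the predictions are 5 × 0.34 = 1.70 and 5 × 0.56 = 2.80, so |d| = 0.55 before and 0 after.

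| | Absolute error | Planned score | Common divisor (2.25) |
|---|---|---|---|
| Emax 0.66 | 0.92 → 0.80 | 0.407 → 0.469 | 0.407 → 0.355 |
| Emax 0.44 | 0.92 → 0.80 | 0.407 → 0.285 | 0.407 → 0.355 |
| Average | 0.92 → 0.80 | 0.407 → 0.377 | 0.407 → 0.355 |

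Both groups gain equally in pain points. On the planned score one group appears to lose 0.062 and the other to gain 0.122. The average gain is 0.030, against 0.052 on a common divisor, so the signal is smaller and varies more between subjects. With s = 0.5 the responsive group's planned score improves as it should (0.275 → 0.235).

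**5. Where the sign changes.** The responsive group's own score worsens once the spread exceeds 39% of its predicted pain: 0.40, 0.53 and 0.67 points at baseline 3, 4 and 5. The average over two equal groups with equal SD worsens only above 0.92, 1.23 and 1.53 points. In the assumed scenarios the responsive group's spread is roughly √[(m·CV)² + (baseline·Emax SD)² + residual variance]. At baseline 5 the smallest is √(0.34² + 0.50² + 0.30² + 0.34²) = 0.76 and the largest √(0.68² + 0.75² + 0.50²) = 1.13. So the responsive group is penalised, while the average still moves the right way.

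**6. Simulated retention among LRT-significant real effects (12 v 12, Emax 0.44 v 0.66).** Two-stage fit with leave-one-out, 6,000 runs in each of the 24 scenarios.

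| One-sided gate test | Planned | Absolute |
|---|---|---|
| Paired t, 0.05 | about 6–29% | about 20–44% |
| Paired t, 0.025 | 3–18% | 12–30% |
| Wilcoxon, 0.05 | 9–37% | 15–41% |

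A common divisor (the prediction without the covariate) performed about the same as absolute error. With Wilcoxon the difference ran from −0.4 to 23 points. It was under 2 points in five scenarios, all with baseline CV 40%.

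**7. Matched strictness.** The planned score also retains fewer false effects. Its t cut-off was therefore relaxed until false retention among LRT-passing null runs equalled that of absolute error. The t-test gap at 0.05 then fell from about 9–28 points to about 2–11.

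**8. Sensitivity.**

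- Age, Emax linear from 0.44 to 0.66 over 18–75 years: t-test 4–13% planned v 12–21% absolute; Wilcoxon 7–18% v 12–21%.
- Mixed-effects likelihood refitted for each left-out subject (three scenarios, baseline 4, 300 runs each): t-test 4% v 16%, 20% v 43%, 5% v 26%; Wilcoxon 15% v 15%, 35% v 41%, 12% v 27%.
- A wider grid of 48 settings, including purely proportional noise, a larger effect and use of the subject's own baseline. Absolute minus planned, two-sided t-test: median +11 points (−6 to +60). Wilcoxon: median +5 (−14 to +51), reversed in 13 of 48. The clear reversals came with purely proportional noise.

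**The case against.** The strongest reply has four parts.

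- **The gate tests all N subjects, not one group.** This stands. A reader might take 39% of predicted pain as the point where the gate fails. It is only where the responsive group's own score turns; the other group offsets it, and the average turns at about 90%.
- **A lower retention rate may only mean a stricter gate.** This stands for more than half of the typical gap, and strictness is what the plan wants. It does not account for all of it. About 2–11 points remain at matched false retention, and one group is scored as worse even when the true parameters are used.
- **The secondary objective is to test for effects, and the LRT does that.** This stands. A reader might infer that the divisor defeats the secondary objective. The plan assigns significance to the LRT, which the divisor does not touch, and a dropped covariate can still be reported as LRT-significant.
- **The cited source for the jackknife may name the test, and every variance is assumed.** Both are fair. The missing test alone would be a matter of detail. The divisor, however, is written out in the plan, and the direction of its effect in step 4 does not depend on the test.

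**Conclusion.** The stated score favours over-prediction and so works against a covariate that correctly lowers predicted pain. The practical loss is moderate. With a paired t-test and additive or combined error, retention of a real 40% Emax effect was lower in every one of the 24 scenarios, but most of the typical gap is strictness. With a rank test or purely proportional noise the loss can be negligible or reversed. The plan expects combined error, where a loss is the usual result.

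The consequence is limited to which covariates enter the final model. The documents do not support the inference that changing the divisor would make the gate sensitive. At N = 24 with absolute error and the 0.05 t-test it still drops about 56–80% of real 40% effects. The percentages rest on assumed variances, time course and gate test. Weight, and effects on C50, steepness, time to peak or baseline pain, were not examined. The direction is firm; the size is illustrative.

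**What to change.** In the Analytical Plan, score both models on the same scale. Either divide both errors by one denominator, for example the prediction without the covariate, or use the mean absolute error in pain points for the excluded subject. In the same edit, name the paired test, its sidedness and its alpha; for example, a one-sided paired t-test at 0.05 on the N per-subject differences, without minus with covariate.

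The cost is two sentences, with the same refits and no new data. There are two downsides. Absolute error gives more weight to high pain, which the common denominator avoids. The gate also becomes somewhat less strict: simulated false retention per covariate–parameter pair (t-test) rises from 0.01–0.08% to at most about 0.20%. If that rate held over three covariates and five parameters, the upper bound would be 15 × 0.20% = 3%, against 15 × 0.08% = 1.2% now.
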